9.1.2. Relationship of Adverse Events to Study Drug

The investigator will provide an assessment of the relationship of the event to the study drug. The possible relationships are “Related” and “Not Related”.

The drug-related TEAE data will be presented by SOC and PT in a manner similar to that described in [Section 9.1.1](#).

9.1.3. Severity of Adverse Event

A summary of TEAEs by CTCAE grade will be presented in a table. The possible severities are 'Mild', 'Moderate', 'Severe', 'Life-threatening' and 'Death related to AE'. In the TEAE severity table, if a subject reported multiple occurrence of the same TEAE, only the most severe will be presented.

The severity of the AE will be graded based on the Common Terminology Criteria for Adverse Events (CTCAE) v5.0. A summary of TEAEs will be provided by treatment arm. Adverse events will be presented by SOC, PT and CTCAE grade in a manner similar to that described in [Section 9.1.1](#).

9.1.4. Serious Adverse Events

Treatment-emergent SAEs will be presented in a table. Drug Related treatment emergent SAEs will also be presented in a table.

The SAE data will be presented by SOC and PT in a manner similar to that described in [Section 9.1.1](#). All SAEs will be summarized and presented in a listing for safety population.

9.1.5. Treatment-Emergent AEs Leading to Treatment Discontinuation

A summary of TEAEs with a study drug action taken of "Drug Withdrawn" will be presented by SOC and PT. At each level of subject summarization, a subject is counted once if the subject reported one or more events. (Note that it is not expected that a subject would have more than one adverse event leading to discontinuation).

The TEAEs leading to treatment discontinuation will be presented by SOC and PT in a manner similar to that described in [Section 9.1.1](#). All TEAEs leading to treatment discontinuation.

9.1.6. Treatment-Emergent Adverse Events Leading to Death

All subjects who have an AE leading to death will be presented in a listing for safety population.

9.1.7. Treatment-Emergent Adverse Events classified as Hypersensitivity Reactions

TEAEs recorded as hypersensitivity reactions in the eCRF will be included. Signs and symptoms of hypersensitivity reactions will be captured on separate eCRF pages. TEAEs classified as hypersensitivity reactions will be summarized as follows:

- Incidence of TEAEs classified as hypersensitivity reactions will be summarized as described in [Section 9.1.1](#)
- TEAEs classified as hypersensitivity reactions by causality will be summarized as described in [Section 9.1.2](#)
- TEAEs classified as hypersensitivity reactions by severity will be summarized as described in [Section 9.1.3](#)
- Serious TEAEs classified as hypersensitivity reactions by severity will be summarized as described in [Section 9.1.3](#)

All hypersensitivity reactions data will be summarized and presented in a listing for safety population.

9.1.8. Treatment-Emergent Adverse Events classified as infusion related reactions (IRR)

TEAEs classified as infusion related reactions (IRR) in the eCRF will be included. Signs and symptoms of IRRs data will be summarized as follows:

- Incidence of TEAEs classified as infusion related reactions (IRR) will be summarized as described in [Section 9.1.1](#)
- TEAEs classified as infusion related reactions (IRR) by severity will be summarized as described in [Section 9.1.3](#)
- Serious TEAEs classified as infusion related reactions (IRR) by severity will be summarized as described in [Section 9.1.3](#)

All IRRs data will be summarized and presented in a listing for safety population.

9.1.9. Treatment-Emergent Adverse Events classified as Anaphylactic Reactions

Anaphylactic Reactions is defined as per [Section 6.3](#) in the protocol.

TEAEs classified as anaphylactic reactions in the eCRF will be included. Signs and symptoms of anaphylactic reactions data will be summarized as follows:

- Incidence of TEAEs classified as anaphylactic reactions will be summarized as described in [Section 9.1.1](#)
- TEAEs classified as anaphylactic reactions by severity will be summarized as described in [Section 9.1.3](#)
- Serious TEAEs classified as anaphylactic reactions by severity will be summarized as described in [Section 9.1.3](#)

All anaphylactic reactions data will be summarized and presented in a listing for safety population. In addition, summary of anaphylaxis criteria will be summarized and presented in listing for safety population.

9.2. Event of Special Interest (EOSI)

Any event of COVID-19 is to be considered as an “Event of Special Interest (EOSI). All EOSI classified by System Organ Class (SOC) and Preferred Term (PT) according to the Medical Dictionary for Regulatory Activities (MedDRA, Version 23.0 or higher or available latest version).

All EOSI will be summarized and presented in a listing for the safety population.

9.2.1. Severity of Event of Special Interest (EOSI)

A summary of EOSI by CTCAE grade will be presented in a table. The possible severities are ‘Mild’, ‘Moderate’, ‘Severe’, ‘Life-threatening’ and ‘Death related to AE’. In the EOSI severity table, if a subject reported multiple occurrence of the same EOSI, only the most severe will be presented.

The severity of the EOSI will be graded based on the Common Terminology Criteria for Adverse Events (CTCAE) v5.0. A summary of EOSI will be provided by treatment arm Adverse events will be presented by SOC, PT and CTCAE grade in a manner similar to that described in [Section 9.2](#)

9.2.2. Serious Event of Special Interest (EOSI)

The Serious EOSI data will be presented by SOC and PT in a manner according to the Medical Dictionary for Regulatory Activities (MedDRA, Version 23.0 or higher or available latest version). All Serious EOSI will be summarized and presented in a listing for safety population.

9.2.3. Event of Special Interest (EOSI) Leading to Death

All subjects who have an EOSI leading to death will be presented in a listing for safety population.

9.3. Clinical Laboratory Evaluations

Clinical laboratory (biochemistry, hematology and urinalysis) test samples will be analyzed at the local laboratory. All summaries and listings will be presented in SI units.

If any laboratory value falls above or below the upper or lower level of quantification, the value of the upper or lower level of quantification will be taken (e.g. <0.5 will become 0.5) for summaries but left as recorded in the listing.

Actual value and change from baseline of all numeric laboratory parameters including clinical chemistry, hematology, urinalysis will be summarized using descriptive statistics in separate tables, by test parameter and visit.

The assessment at Day 1 and Day 15 for all the laboratory parameters will be conducted before the treatment administration.

All relevant clinical laboratory tests will be interpreted as below.

- Abnormal, Decreased, Clinically Significant
- Abnormal, Decreased, Not Clinically Significant
- Normal
- Abnormal, Increased, Clinically Significant
- Abnormal, Increased, Not Clinically Significant

These categorical data will be summarized in shift tables comparing the results at each scheduled post-baseline visit with those at the baseline visit. A row denoted “Missing” will be included in count tabulations where specified on the shells to account for dropouts and missing values.

The denominator for all percentages will be the number of subjects in that treatment within the safety population. Unless otherwise specified, baseline will be defined as the last non-missing evaluation prior to or on the date that the first dose of treatment is taken.

The numeric parameters will be graded using CTCAE v5.0, where applicable. The CTCAE grades for analysis will be Grade 1 (Mild), Grade 2 (Moderate), Grade 3 (Severe) and Grade 4 (Life-threatening). The CTCAE Grade 5 (Death) will not be applied in this analysis since death cannot be determined from a numeric laboratory result. Unit conversion will be performed if the clinical laboratory unit is not consistent with the unit in CTCAE v5.0. These grades will be summarized in shift tables comparing worst post baseline visit grade with those at the baseline visit.

The number and percentage of subjects will be summarized by CTCAE term and CTCAE grade for the safety population, where this summary includes only the most severe case during the overall post-baseline visits. All hematology, biochemistry and urinalysis data will be listed in separate listings along with clinical significance and normal range flags (where applicable) for the safety population.

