5.2.3 Study Treatment Administration

Study treatments (DRL_RI or US-rituximab/EU-rituximab) will be administered by IV infusion using the escalating infusion rate described in the Health Authority-approved product

labels for US-rituximab/EU-rituximab. The infusion rate must be well controlled to reduce the incidence of serious IRRs.

Only qualified personnel who are familiar with procedures that minimize undue exposure to them and to the environment should undertake the preparation, handling, and safe disposal of biological agents.

Study treatment infusions should be administered under close medical supervision and in an environment where full resuscitation facilities are immediately available. Vital signs will be monitored every 30 minutes (\pm 5 minutes) during the course of the treatment administration or more frequently as necessary.

The study treatments will be administered as two 1000 mg IV infusions on Day 1 and Day 15.

Below instructions should be followed in consolidation with the local product labelling if it differs from these instructions.

- **First infusion (Day 1):** Initiate infusion at a rate of 50 mg/hour. In the absence of infusion toxicity, increase infusion rate by 50 mg/hour increments at 30-minute intervals, to a maximum of 400 mg/hour.
- **Second infusion (Day 15):** Initiate infusion at a rate of 100 mg/hour. In the absence of infusion toxicity, increase rate by 100 mg/hour increments at 30-minute intervals, to a maximum of 400 mg/hour.
- Subjects should be closely monitored post-dose for at least 1 hour for the onset of IRRs. Subjects who develop evidence of severe reactions, especially severe dyspnea, bronchospasm, or hypoxia should have the infusion interrupted immediately. In all subjects, the infusion should not be restarted until complete resolution of all symptoms and normalization of laboratory values is achieved. At this time, the infusion can be initially resumed at not more than one-half the previous rate. If the same severe reactions occur for a second time, the decision to stop the treatment should be seriously considered on a case-by-case basis.
- Mild to moderate IRRs usually respond to a reduction in the rate of infusion. The infusion rate may be increased upon improvement of symptoms.

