7.4 Statistical Analysis Methodology

7.4.1 General Principles

The statistical analysis will be performed using SAS Version 9.4 or later.

The immunogenicity and safety data will be analyzed descriptively. All individual data as well as results of statistical analyses, whether explicitly discussed in the following sections or not, will be presented in individual subject data listings and statistical summary tables.

In general, continuous variables will be summarized using the following standard descriptive summary statistics: number of observations, arithmetic mean, standard deviation, minimum, median, and maximum. Categorical variables will be displayed by means of frequency tables including percentages.

Baseline is defined as the last non-missing pre-dose assessment. Overall summaries and analyses will be performed based on data pooled from all sites.

A SAP will be prepared and finalized before the clinical study database is closed.

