3.1. Overall Study Design and Plan

This study is a phase 3, randomized, double-blind, parallel group, multicentre study to assess the immunogenicity and safety of two 1000 mg IV infusions of DRL₁RI or continued treatment with Rituxan[®] or MabThera[®] in approximately 140 subjects (70 per treatment arm) in transitioning to biosimilar Rituximab (DRL₁RI) or continued treatment with Rituxan[®] or MabThera[®].

Baseline is defined as the last available value prior to the first dose of study drug administration. For Vital Sign timepoint assessment are scheduled on Day 1 and Day 15, if the time is missing then Day 1 Pre-dose will be considered as baseline.

The study will include screening period (Days -14 to 0) and a double-blind period (Day 1 to Week 12), which consist 2 weeks of treatment period and 10 weeks of follow-up period for safety and immunogenicity. An additional follow-up visit will be conducted at Week 26 to evaluate safety and to perform a serum pregnancy test in women of childbearing potential (WOCBP).

Re-screening will be allowed for those subjects who do not meet the criteria for participation in this study (screen failure) at the investigator's discretion, following discussion with the sponsor designee medical monitor.

Eligible subjects will be randomized in permuted blocks in 1:1 ratio by interactive web response system (IWRS) to receive either two 1000 mg infusions of DRL_RI (Arm A) or US-rituximab/EU-rituximab (Arm B) on Day 1 and Day 15. Randomization schedule will be stratified by region (US/EU).

[figure not shown]
Subjects having signed the informed consent form (ICF) versions prior to the protocol version 3.0, Amendment 2 need to re-consent to continue participating in the study after Week 12 through Week 26. If a subject does not re-consent for further study participation after Week 12, then his/her study data up to Week 12 will be collected and the subject will be discontinued from the study.

Study procedures include physical examination, vital signs measurement, clinical laboratory assessments, AEs, and concomitant medication. All subjects completing the study at Week 12 or those discontinuing the study before Week 12 will attend an EOS/early termination (ET) visit. Furthermore, subjects completing the follow-up at Week 26 or discontinued after Week 12 will attend Week 26/early termination (ET) visit.

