Continuous data will be described using descriptive statistics (i.e. n, mean, standard deviation [SD], median, quartiles, minimum, and maximum). Categorical data will be described using the count and percentage in each category. For the summary statistics of all numerical variables unless otherwise specified, minimum and maximum will be displayed to the same level of precision as reported. Mean and median will be displayed to one level of precision greater than the data collected. Standard deviation will be displayed to two levels of precision greater than the data collected.

When count data are presented, the percentage will be suppressed when the count is zero in order to draw attention to the non-zero counts. A row denoted “Missing” will be included in count tabulations where specified on the shells to account for missing values. The denominator for all percentages will be the number of subjects within the analysis population of interest, unless otherwise specified. Percentages will be presented to one decimal place.

For Time Matched Rituximab Concentrations (TMRC) sample, concentration below the lower limit of quantification (BLLOQ) will be converted to '0' for the purpose of quantitative summaries, but will be presented as recorded, i.e. BLLOQ in listings.

Data will be displayed in all listings sorted by subject number and visit, if applicable. Listings will include all visits including unscheduled visits.

"No data available for this report" will be presented when there are no data available to report.

Unless otherwise specified, baseline will be defined as the last non-missing value collected before the first study drug administration. Study day is defined as:

- Visit/examination date – date of first study drug administration when date is prior to the date of first study drug administration (day 1).
- Visit/examination date – date of first study drug administration + 1 when date is on or after day 1.

For summaries by visit, if multiple records fall on the same visit and timepoint, then the record which is the earliest value will be chosen.

Unscheduled results will not be summarized but will be listed, unless otherwise specified. Post baseline summaries will include all values collected after the date of first study drug administration.

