9.4. Vital Sign Measurements

Vital sign will be conducted at screening, on Day 1, Day 15, and at Weeks 4, 8, 12 (EOS/ET) and Week 26 visits. At Day 1 and Day 15 the Vital signs will be assessed every 30 minutes (\pm 5 minutes) during and end of infusion at time points Pre-dose, 30 min, 1 hr, 1.5 hrs, 2 hrs, 2.5 hrs, 3 hrs, 3.5 hrs, 4 hrs, 4.5 hrs, 5 hrs, 5.5 hrs, 6 hrs, 6.5 hrs, 7 hrs, 7.5 hrs and 8 hrs.

A summary table with actual values and change from baseline will be presented for vital sign data (systolic blood pressure (mmHg), diastolic blood pressure (mmHg), heart rate (beats/min), respiratory rate (breaths/min) and oral temperature ($^{\circ}$ C)) by scheduled visit and time point.

The indicative reference ranges for Systolic blood pressure: 90 – 140 mm Hg; Diastolic blood pressure: 50 – 90 mm Hg; Heart rate: 60 – 100 beats/min; Respiratory rate: 12 – 20 breaths/min; Temperature: 36 – 37.2 $^{\circ}$ C. Based on the ranges the parameters will be interpreted as below.

- Abnormal, Decreased, Clinically Significant
- Abnormal, Decreased, Not Clinically Significant
- Normal

- Abnormal, Increased, Clinically Significant
- Abnormal, Increased, Not Clinically Significant

A shift table comparing the interpretation at scheduled post-baseline visit and time point with those at baseline will be presented by visit and time point for the safety population.

All vital sign data will be listed by visit for safety population.

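### SAP 9.3 sets laboratory baseline by date and SAP 4 starts post-baseline after that date; read literally, a post-dose Day 1 value could be baseline, and SAP 4 conflicts with the Day 1 vital-sign tables in SAP 9.4

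*SAP*

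**What the plan says.** Four places define baseline.

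- Protocol 7.4.1: "Baseline is defined as the last non-missing pre-dose assessment".
- SAP 3.1: "Baseline is defined as the last available value prior to the first dose of study drug administration".
- SAP 4, General Statistical Considerations: "baseline will be defined as the last non-missing value collected before the first study drug administration".
- SAP 9.3, for laboratory data: "baseline will be defined as the last non-missing evaluation prior to or on the date that the first dose of treatment is taken".

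The first three are strictly pre-dose. The fourth admits any value dated on the day of the first dose.

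SAP 4 also sets where post-baseline begins: "Post baseline summaries will include all values collected after the date of first study drug administration". It adds that unscheduled results are listed rather than summarized unless specified otherwise, and that by-visit summaries take the earliest record when several share a visit and time point.

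On timing, SAP 9.3 states: "The assessment at Day 1 and Day 15 for all the laboratory parameters will be conducted before the treatment administration". The schedule of events lets the Day 1 laboratory sample be drawn a day before dosing. SAP 9.4 lists Day 1 vital-sign time points at pre-dose and then every half hour to 8 hours. It plans change from baseline by visit and time point, and "A shift table comparing the interpretation at scheduled post-baseline visit and time point with those at baseline".

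**The concern.** The two date rules reinforce each other. A laboratory value obtained after the first infusion has started, but on the same calendar day, meets the SAP 9.3 definition of baseline and fails the SAP 4 definition of post-baseline. It would also be left out of the worst post-baseline CTCAE grade.

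Such a value is foreseeable in a subject who reacts. Protocol 5.2.3 says that after a severe reaction "the infusion should not be restarted until complete resolution of all symptoms and normalization of laboratory values is achieved", which presupposes laboratory tests during the Day 1 visit. Protocol 6.1 allows unscheduled assessments. If the last value that day is abnormal, later visits show no worsening or an apparent improvement. If it is a normalised repeat, the abnormal value before it is neither baseline nor post-baseline.

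For vital signs the trouble is a contradiction. SAP 9.4 intends to tabulate the Day 1 infusion readings against baseline, while the general sentence in SAP 4 does not admit them as post-baseline. Protocol 5.2.2 says that acute reactions are seen most often at the first infusion, so these readings matter.

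SAP 10.1 lists only the addition of estimands as a change from the protocol. The different laboratory baseline is therefore not declared.

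**Working it through.** No sample size, power or error rate is involved. The check sets the rules side by side and then makes three small counts.

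**1. Which baseline rule governs laboratory data?** The SAP 4 and SAP 9.3 sentences both carry a proviso that they yield where something else is specified. SAP 9.3 is the specific section, so the natural reading is that it governs laboratory data. The SAP 3.1 sentence has no proviso, so one can also argue that SAP 9.3 yields to it. The text does not settle this.

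**2. How each type of Day 1 value is classified.**

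| Value | Protocol 7.4.1, SAP 3.1, SAP 4 | SAP 9.3 | Post-baseline under SAP 4, read literally |
|---|---|---|---|
| Scheduled Day 1 blood, pre-dose | can be baseline | can be baseline | no |
| Blood on Day 1 after infusion start | cannot be baseline | can be baseline | no |
| Day 1 vital signs, 30 min to 8 h | cannot be baseline | does not apply | no, although SAP 9.4 tabulates them |

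Only rows two and three are in trouble. The number of laboratory samples scheduled after dosing on Day 1 is 0, so row two needs an unscheduled same-day test or a scheduled sample taken late. SAP 4 keeps unscheduled results out of summaries but does not say whether one may be selected as baseline. Its earliest-record rule pulls against the last-value rule of SAP 9.3.

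**3. How many subjects could have such a laboratory value?** The protocol gives no rate for same-day reaction bloods, so its infusion-reaction figures (Protocol 1.1.1.4) serve as a proxy, with 140 planned subjects.

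- Serious reactions: 17/3189 = 0.53%; 0.0053 × 140 = 0.7, or about 1 subject.
- Any reaction at the first infusion of first exposure: 733/3189 = 23.0%; 0.230 × 140 = 32 subjects.

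The second figure is not a realistic estimate. It would require bloods in every subject with a reaction of any grade. It also comes from first exposure, whereas every subject here has had a prior course, a history of hypersensitivity to rituximab is excluded, and the protocol says reactions decline with later infusions. The first figure is closer to the group in whom Protocol 5.2.3 ties restarting to laboratory values. With 70 per arm, one subject is 1/70 = 1.4% of an arm.

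**4. How many vital-sign time points are touched?** From 0.5 h to 8 h in half-hour steps, SAP 9.4 lists 8/0.5 = 16 Day 1 time points after pre-dose. Not all will be filled. At the Day 1 rates in Protocol 5.2.3, without interruption:

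- The first seven half-hours, at 50 to 350 mg/h, deliver 25 + 50 + 75 + 100 + 125 + 150 + 175 = 700 mg in 3.5 h.
- The remaining 300 mg at 400 mg/h takes 300/400 = 0.75 h.
- The total is 3.5 + 0.75 = 4.25 h.

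The listed points within 4.25 h run from 0.5 h to 4.0 h, which is 8. Protocol 6.3.6 asks for readings during the infusion, at its end and as clinically indicated. The later slots will therefore be filled mainly in subjects whose infusion was slowed or interrupted.

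**The case against.** The strongest reply is that the plan's specific text already prevents most of this. Scheduled Day 1 bloods precede treatment, unscheduled results are only listed, and the earliest-record rule would favour the pre-dose sample. For vital signs, SAP 9.4 names the Day 1 time points and plans tables for them, SAP 3.1 fixes Day 1 pre-dose as baseline if the time is missing, and the SAP 4 sentence says what will be included without saying that nothing else will be.

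Much of that stands, and it rules out several stronger inferences.

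- *Any Day 1 test taken during a reaction becomes baseline.* The documents do not support this. It can happen only through an unscheduled or late sample, and only if such a sample is eligible for selection, which is not stated.
- *Day 1 infusion vital signs are dropped.* They are not. One general sentence conflicts with a specific plan to report them.
- *The plan hides infusion reactions.* It does not. Infusion-related, hypersensitivity and anaphylactic reactions are primary safety endpoints, taken from their eCRF classification and counted as treatment-emergent from the first dose (SAP 9.1 and 9.1.7 to 9.1.9). Protocol 6.3.2 requires abnormal results with symptoms, intervention or treatment interruption to be reported as adverse events. All values are listed.

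The reply does not remove the conflict. Keeping unscheduled results out of summaries is not the same as barring them from serving as baseline, and the earliest-record rule is written for by-visit summaries. Because the scheduled blood may be drawn the day before dosing, a reaction-driven sample could be the only one dated Day 1. SAP 9.4 does not say that it overrides SAP 4. A programmer following the text would have to choose.

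**Conclusion.** The point holds as a narrow inconsistency that should be corrected. The date-based laboratory baseline in SAP 9.3 contradicts the pre-dose definition in Protocol 7.4.1, SAP 3.1 and SAP 4. The date-based start of post-baseline in SAP 4 contradicts the Day 1 vital-sign tables in SAP 9.4.

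The laboratory effect is small. About 1 of 140 subjects is affected if same-day reaction bloods occur at the serious-reaction rate. That rests on treating a serious reaction as a stand-in for the severe reactions of Protocol 5.2.3, and on carrying a rate from the reference product's trials over to this re-treated population. Late scheduled samples would add to it, and the documents give no rate for them.

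The vital-sign conflict reaches every subject dosed, with 16 listed Day 1 time points, about 8 of them within an uninterrupted infusion. It has consequences only if SAP 4 is programmed literally.

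Both effects are confined to the laboratory and vital-sign summaries, which are among the other safety endpoints. The adverse-event analyses are untouched.

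**What to change.** Make these changes before database lock.

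1. In SAP 9.3, replace the baseline sentence with the Protocol 7.4.1 rule: the last non-missing value before the start of the first infusion. If the sample time is missing, use the scheduled Day 1 pre-dose value, as SAP 3.1 already does for vital signs.
2. In SAP 4, define post-baseline as any value after the start of the first infusion, so that it agrees with SAP 9.4.
3. State that unscheduled post-dose values cannot serve as baseline and do count in the worst post-baseline CTCAE grade. Without this, the general rule on unscheduled results would still keep reaction-driven bloods out of the summaries.

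The cost is a few sentences and minor reprogramming. The one practical limit is that the documents do not say that laboratory sample times are collected. Where they are not, the scheduled pre-dose label is the fallback. The baseline change restores the protocol's own definition, so it needs no protocol amendment.
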